8.8.7. The MOS Social Support Survey

The MOS Social Support survey (Sherbourne & Stewart, 1991) is a 20-item self-report measure of social support. Each item is presented as a 5-point Likert scale anchored from 1 (none of the time) to 5 (all of the time). The MOS Social Support Survey yields four subscale scores: emotional/informational support, tangible support, affectionate support, and positive social interactions. Each subscale is associated with excellent internal consistency reliability ($\alpha > .91$) (Sherbourne & Stewart, 1991). The MOS Social Support Survey is associated with good convergent validity with measures of family ties, family functioning, and mental health and good divergent validity with measures of purely physical health (Sherbourne & Stewart, 1991).

8.8.8. The Difficulties in Emotion Regulation Scale

The Difficulties in Emotion Regulation Scale (Gratz & Roemer, 2003) is a 36-item self-report measure of six dimensions of emotion regulation difficulties: lack of awareness of emotional responses, lack of clarity of emotional responses, non-acceptance of emotional responses, limited access to emotion regulation strategies perceived as effective, difficulties controlling impulses when experiencing negative emotions, and difficulties engaging in goal-directed behaviours when experiencing negative emotions. Each item is presented as a 5-point Likert scale anchored from 1 (almost never) to 5 (almost always). The global difficulties in emotional regulation scale is associated with excellent internal consistency reliability (α = .93) and each subscale is associated with good internal consistency reliability (α > .80) (Gratz & Roemer, 2003). The difficulties in emotion regulation scale is associated with good construct validity and predictive validity (Gratz & Roemer, 2003).

8.8.9. The Miller Behavioural Style Scale

The Miller Behavioural Style Scale – Short Form (Miller, 1987; Steptoe, 1989) is a self-report measure of information seeking preferences. The scale identifies individual preferences for seeking threat-related cues (monitors) versus seeking distraction to minimise exposure to threat-related cues (blunters). The scale prompts participants to imagine two stressful scenarios, each of which is followed by eight statements that describe different ways of coping with the stressor. Participants are asked to select all statements that apply to them. The Miller Behavioural Style Scale is associated with good test-retest reliability over a 4-month period (r = 0.72 for the monitoring subscale and r = 0.75 for the blunting subscale) (Miller, 1987). The Miller Behavioural Style Scale is associated with high construct validity, as

Finding My Way UK

indicated by high correspondence with information-seeking behaviour in a stress-inducing laboratory task (Miller, 1987).

8.8.10. The CompACT

The CompACT (Francis et al., 2016) is a 23-item self-report measure of psychological flexibility. Each item is presented as a 7-point Likert scale anchored from 0 (strongly disagree) to 6 (strongly agree). The CompACT is associated with adequate internal consistency reliability (average inter-item correlation, r = 0.34) (Francis et al., 2016). The CompACT is associated good convergent validity with another measure of Acceptance and Commitment Therapy processes and good discriminant validity with a measure of Social Desirability (Francis et al., 2016).

8.8.11. The Self-Help Compliance Scale

The Self-Help Compliance Scale (Thiels et al., 2001) is a brief measure assessing engagement with self-guided psychological interventions. The scale consists of 3 items presented on a 5-point Likert-type scale assessing the amount of information participants read, the number of suggestions and worksheets participants completed, and how much time participants spent using the programme. The questionnaire also includes one open question asking participants what other psychological treatment they have received during the programme.

8.9. Withdrawal Criteria

Other than death or other unforeseen loss of capacity to consent, there are no criteria which will cause the investigator to withdraw any participant from the clinical trial. Participants will be informed that they do not have to complete any online modules they do not wish to, and that they can withdraw themselves from the clinical trial at any time. Participants can skip questions within the self-report measures, but this may mean we can't include them in the analysis. Instructions for addressing missing data differ among the psychometric measures and our decision to exclude any participant from an analysis will therefore depend on which item responses are missing.

8.10. End of Trial

Our recruitment target is 294 participants, although we may over-recruit by up to 30% in order to mitigate the effects of missing data and to allow for at least minimal recruitment of less common cancer types. We will stop recruitment on 28th February 2022. The trial will end after the last participant has completed all study activities.

9. INTERVENTION UNDER INVESTIGATION

9.1. The UK-Adapted Finding My Way Programme

Finding My Way is an online Cognitive Behavioural Therapy-based intervention specifically tailored to the needs of cancer patients. The Finding My Way programme is composed of six modules, which address the following topics:

- 1) Starting treatment: This module provides guidance on working with the medical team, including assertive communication and decision making.
- 2) Coping with physical symptoms and side effects: This module provides information about fatigue, pain, and insomnia and provides activity pacing worksheets and relaxation audio-tracks.
- Coping with emotional distress: This module covers depression, anxiety, anger and stress and includes both cognitive restructuring worksheets and mindfulness audiotracks.
- 4) Body image, identity, and sexuality: This module includes psychosexual worksheets and therapeutic writing activities.
- 5) Your family and friends: This module provides further guidance on assertive communication and needs assessment worksheets.
- 6) Completing treatment: This module includes self-management strategies to facilitate healthy lifestyles.

One new module is made available to participants each week, such that the Finding My Way Programme runs over a total of six weeks. The programme also includes one booster module summarizing key strategies, which is made available to participants one month after the completion of the main six-week programme. The full intervention content is listed in Appendix X.

Finding My Way UK will run in the same format as the original Australian Finding My Way programme, including the same modules presented in the same time-order. The version of the Finding My Way programme implemented in the current study will include minor adaptations for the UK context (including signposting to UK-relevant resources and video interviews with British cancer survivors).

The original Australian Finding My Way programme can be found at the following link: www.findingmyway.org.au. Access to the programme is free, but users are required to first register an account. The UK version will have restricted access during this trial and account registration will be limited only to trial participants.

9.2. Assessment of Compliance with Finding My Way UK Programme

Compliance with the Finding My Way intervention will be measured via the following website use indicators:

- a) The number of logins to the website;
- b) Total amount of time logged in;
- c) Number of intervention modules completed;
- d) Number of worksheets completed; and
- e) Responses to the Self-Help Compliance Scale.

10. ADVERSE EVENTS

10.1. Procedures for Eliciting Reports of and Recording and Reporting Adverse Events

We recognise that some of the modules may bring up challenging material related to emotional distress, psychosexual needs, and relationship concerns. We will, therefore, signpost participants to a range of relevant resources, including 24-hour crisis hotlines, within the Participant Information Sheet, on the welcome page when they first log in to the Finding My Way UK website, and within the specific modules that cover challenging material, including the booster module. The participant can navigate back to this web page of resources at any point during the Finding My Way UK programme. Within the Participant Information Sheet, we will also encourage participants to speak to their GP and clinical care team regarding any mental health concerns that arise, or that they become aware of, during the study.

Within the Participant Information Sheet, we will also ask participants to contact the research team if any of the material causes distress. The research team will note this finding down in a database of adverse events and inform the sponsor of all new adverse events recorded in the study. Each time the research team informs the recruiting site of a newly-received consent form, the research team will also send additional material specifying that the clinical team should inform the research team of any distress the participant mentions that has arisen from intervention content. We will request that each clinical team also asks the participant to report these adverse events to the research team directly.

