	 To determine the effects of the UK-adapted Finding My Way programme on psychological adjustment to cancer. To determine the effects of the UK-adapted Finding My Way programme programme on health service utilisation. To determine whether social support, vulnerability to distress, and motivation to seek information moderate the effects of the UK-adapted Finding My Way programme programme on primary and secondary study endpoints. To determine whether psychological flexibility mediates the effect of the UK-adapted Finding My Way programme on cancer-specific distress.
	We will also conduct exploratory analyses testing the potential moderating effects of clinical and demographic variables on primary and secondary study endpoints.
Investigational product	A six-week online programme of cancer-specific cognitive- behavioural therapy modules, plus one additional booster module
Comparator	Waitlist control: This information group will initially receive an information pack informing them of resources already available to cancer survivors in the UK. After the 6-month follow-up questionnaire has been completed, they will then be granted access to the Finding My Way programme.
Maximum Duration of Treatment	The Finding My Way programme includes 6 weeks of content, plus an additional booster module presented one month after initial treatment completion. Participants will continue to be able to access website content for an additional 4 months after the final participant has completed all study-related activities.

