8.7.8. Clinical Data Collection

The following clinical data will be extracted from participants' medical records:

- Date of diagnosis;
- Primary or recurrent cancer;
- Whether the participant was treated with curative or palliative intent;
- The treatment approach adopted for the participant (surgery, chemotherapy, radiotherapy, or watch-and-wait);
- Date of the end of active treatment (if treatment has ended at this point);
- The date of any recurrence or relapse (if applicable);
- Date of death (if applicable);
- Whether the participant received referral to a mental health care professional since their diagnosis of cancer;
- The number of days of inpatient care since study enrolment, and types of healthcare professionals seen during these stays;
- The number of outpatient visits since study enrolment, and types of healthcare professionals seen during these visits; and
- Any diagnosis tests conducted since study enrolment.

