11.2.3. Efficacy Analyses

The analytic plan matches the Australian FMW RCT exactly (Beatty et al., 2019). Data analyses are powered to undertake Mixed Model Repeated Measures analyses to examine intervention effects on change from baseline to follow-up for each outcome (intention-to-treat analysis). Two models will be run for each outcome: (i) unadjusted, accounting for co-variance of baseline measures of outcomes; and (ii) fully adjusted, controlling for all potential confounding variables assessed. Sensitivity analyses will evaluate the effects of missing data. Cohen's *d* effect sizes reflect intervention effects, and clinically significant changes will be assessed using Reliable Change Indices.

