11.5. Criteria for Terminating the Study

No interim analysis is planned. The study will be terminated prematurely only on the grounds of exceptional, unforeseen safety concerns or exceptional, unforeseen recruitment issues.

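### Adverse events are elicited only as distress attributed to the programme, so their counts cannot be compared between arms, and no arm-neutral count of patients who deteriorate is named as a harm measure

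*Protocol*

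**What the plan says.** Section 10.1 of the protocol is the procedure for eliciting, recording and reporting adverse events, and it gives two routes. In the first, the Participant Information Sheet will "ask participants to contact the research team if any of the material causes distress". For such reports, "The research team will note this finding down in a database of adverse events". In the second, each recruiting site is told to pass on "any distress the participant mentions that has arisen from intervention content".

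The control group will "initially receive an information pack informing them of resources already available to cancer survivors in the UK" (section 1). Programme access follows only after the 6-month follow-up (sections 1 and 5).

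Four other places bear on the point:

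- Section 11.2.3, under efficacy: "clinically significant changes will be assessed using Reliable Change Indices". Deterioration is not mentioned.
- Section 8.7.8: date of death and other record data are extracted for all participants.
- Section 14.1: investigators must tell the ethics committee of adverse experiences that are serious or not expected. This is not limited to programme content.
- Section 11.5: apart from recruitment problems, the study may be "terminated prematurely only on the grounds of exceptional, unforeseen safety concerns". The opening section on roles states that there is no formal data monitoring committee.

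**The concern.** Both routes require someone to judge that the programme caused the distress before it is reported. A waitlist patient has no programme to blame during the comparison. A small count in the intervention arm therefore cannot show absence of harm, and a larger one cannot be set against the background worsening to be expected in recently diagnosed patients.

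This matters because the protocol itself expects some modules to raise difficult material (3.1 and 10.1). It also supports its minimal-risk rating by noting that the earlier Australian trial identified no adverse effects. A low count here invites the same reading without any comparison behind it.

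The planned comparison of means covers average worsening. It averages over patients who improve and patients who deteriorate, so a group that does badly can be hidden.

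**Working it through.** The protocol states no adverse-event rate or harm calculation, so there is no figure of that kind to reproduce. The check has three parts.

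**1. What each source can show by arm before waitlist access**

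| Source | Intervention | Waitlist | Comparable? |
|---|---|---|---|
| Site reports (10.1) | content-attributed distress | no content, so zero | no |
| Participant reports (10.1) | distress caused by the material | zero or near zero | no |
| Post-Traumatic Stress Scale, DASS-21 (1.3, 8.7.2 to 8.7.7) | five time points | five time points | yes |
| Date of death (8.7.8) | from records | from records | yes |

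**2. What a naive comparison of the log would do.** Take 147 per arm with the waitlist count at 0. Five reports against none give a Fisher exact p of 0.060, and six against none give 0.030. Six content-attributed reports would thus reach nominal significance because of how reports are elicited, with no evidence that distress was more frequent in one arm.

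**3. What an arm-neutral count could deliver.**

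Inputs: SD 7 and correlation 0.7 between measurements (11.1); internal consistency .91 for the Post-Traumatic Stress Scale (8.8.2); 147 per arm with 20% attrition (11.1), so 147 × 0.8 = 117.6, taken as 118 completers.

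- SD of change = 7 × √(2 × (1 − 0.7)) = 5.42, which reproduces the value in 11.1.
- Reliable-change threshold = 1.96 × √2 × 7 × √(1 − 0.91) = 5.82 points.
- With no mean change and normal change scores, P(worsening > 5.82) = P(Z > 5.82/5.42) = 0.1415, or 0.1415 × 118 = 16.7 patients per arm.
- Half-width of the 95% CI for the risk difference at equal rates = 1.96 × √(2 × 0.1415 × 0.8585/118) = 0.089, about 9 percentage points.

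Sensitivity to the correlation, with the threshold unchanged:

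| Correlation | Rate per arm | CI half-width |
|---|---|---|
| 0.5 | 20.3% | ±10.3 points |
| 0.7 | 14% | ±9 points |
| 0.8 | 9.4% | ±7.5 points |

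As a second view, with 118 per arm, two-sided 0.05 and 80% power, assumed control rates of 5%, 10%, 15% and 20% require intervention rates of about 16%, 24%, 30% and 36% for detection.

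**The case against.** The strongest reply is that the expected harm is emotional distress, and distress is the primary endpoint. It is measured in both arms, compared by intention to treat (11.2.1) and tested against a non-directional alternative (11.2.2). A reader might infer from 10.1 that the trial cannot say whether the programme does harm. The documents do not support that: average worsening would show in the planned analysis, and Reliable Change Indices could count deterioration.

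Two other strong readings also fail. One is that adverse events are formally defined as programme-caused distress. Section 10.1 restricts what is elicited and gives no definition, and 14.1 uses wider language, though without a route for collecting such events. The other is that the waitlist arm cannot have any reports at all. The reference to the material, in an information sheet that both arms receive, could be stretched to the information pack or the questionnaires, and waitlist patients do receive the programme later. At or near zero during the comparison is the fair description.

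It may also be said that tabulating deterioration by arm is a matter for the SAP, which is not at hand, and that no passage plans a comparative safety claim from the log. Both points have force and limit the weight of the concern. They do not remove it: the attribution rule is stated in the protocol, and the log it produces cannot serve as two-arm harm data. Finally, the 14% is background movement shared by both arms, not a harm rate, and the calculation describes the replacement rather than the defect. That is correct, and it is used here only to show what precision to expect.

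**Conclusion.** The point holds for the adverse-event log. During the randomised comparison one arm is at or near a structural zero, so the counts support no between-arm statement in either direction. It does not extend to the trial as a whole, because mean worsening in distress is covered by the efficacy analyses. The gap is a patient-level harm measure obtained in the same way in both arms, and the planned data can fill it with modest precision: about ±9 points if 14% deteriorate, and ±7.5 to ±10.3 points for correlations from 0.8 to 0.5. These figures assume normal change scores on a bounded 0 to 51 scale (17 items scored 0 to 3), a reliability taken from the scale's validation study, and attrition as planned. This is a worthwhile, inexpensive improvement and not a flaw in the primary analysis.

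**What to change.** In 11.2.3, name reliable deterioration on the Post-Traumatic Stress Scale, meaning worsening beyond the Reliable Change Index, as the main harm measure at post-treatment and at the 3- and 6-month follow-ups, all before waitlist access. Add the DASS-21 scales as supportive, and deaths since enrolment. Tabulate by arm with a risk difference and 95% CI, and state that only large excesses can be detected.

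In 10.1, keep content-attributed reports as a separate descriptive listing and state that no comparative safety conclusion is drawn from it. Reconcile the elicitation wording there with the broader reporting duty in 14.1.

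Do not use the mental-health referral item as a harm outcome. It records "Whether the participant received referral to a mental health care professional since their diagnosis of cancer", so it mixes referrals before and after randomisation. A referral may also reflect benefit, since 3.1 says the programme supports patients in activating existing clinical and social support.

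The cost is one extra descriptive table from data already planned and a few sentences of text. The downside is several unadjusted comparisons with limited precision, so the Post-Traumatic Stress Scale should be marked as the lead measure.

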11. STATISTICAL AND DATA ANALYSIS

11.1. Sample Size Calculation

Calculations are based on the primary outcome of change in cancer distress between the two patient groups. The original FMW randomised clinical trial sample size calculation used a standardised effect size of 0.35 and standard deviation of 4 units, which equates to an absolute change in cancer distress scores of 1.4 units. This study observed a larger than expected standard deviation and we propose a sample size based on a conservative estimate of the residual standard deviation of 7 units accordingly (but keeping the clinically relevant difference at the aforementioned 1.4 units). Correlation between successive measurements on the same patient are assumed to be high and a conservative r=0.7 is used. Sample size calculations are performed assuming a paired t-test using a derived standard deviation about the change in the primary outcome of 5.42. Assuming a patient attrition of 20% and a two-sided alpha=0.05, then 294 patients (147 per study arm) are required for statistical power of 80%.

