1. STUDY SYNOPSIS

Name of Sponsor	North West Cancer Research								
Name of Investigational Product:	Finding My Way: An online cognitive behavioural therapy-based psychological intervention for cancer survivors								
Title of Study:	Finding My Way UK: Adaptation and Replication Testing of the Benefits of Online Psychological Support for Cancer Survivors								
Medical Condition Under Investigation:	Cancer (Of all sites)								
Study centres	Multi-centre study in England								
Protocol Number:									
Study Design:	Randomised, investigator-blind, waitlist-controlled study to determine the efficacy of an online cognitive behavioural therapy-based intervention in improving psychological outcomes in cancer survivors								
Planned Sample Size:	294 participants in total (in order to achieve 147 participants per study arm)								
Trial Subjects Selection Criteria:	 Inclusion criteria: The subject must satisfy the following criteria for entry into the study: Been diagnosed with cancer in the past six months Have received anti-cancer treatment with curative intent Aged 16 years or over Sufficiently proficient in English to provide informed consent and use the online programme Able to access the internet Currently have (or willing to set up) an active email address Exclusion criteria: Patients will be excluded from the study if any of the following applies: Severe comorbidity considered by the screening nurse to interfere with the individual's ability to complete the requirements of the study or provide informed consent (e.g., intellectual disability or neurological impairment). 								
Study Objectives:	Primary To determine whether the UK-adapted Finding My Way programme reduces cancer-specific distress. Secondary To determine the effects of the UK-adapted Finding My Way programme on anxiety, depression, and general stress. To determine the effects of the UK-adapted Finding My Way programme on quality of life.								

	T

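### Section 11.1 sizes a between-arm comparison with a paired, one-group t-test; at a single visit, after the stated 20% attrition, 147 per arm gives about 51% power (57% baseline-adjusted), not 80%

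*Protocol*

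**What the plan says.** Protocol section 11.1 frames the question as one between arms: "Calculations are based on the primary outcome of change in cancer distress between the two patient groups". It takes the target difference from the Australian trial's planning values, a standardised effect of 0.35 with an SD of 4, "which equates to an absolute change in cancer distress scores of 1.4 units". It then raises the variability to a "conservative estimate of the residual standard deviation of 7 units accordingly" and, for the correlation between successive measurements, says "a conservative r=0.7 is used". The test follows: "Sample size calculations are performed assuming a paired t-test using a derived standard deviation about the change in the primary outcome of 5.42". With 20% attrition and two-sided alpha of 0.05, it concludes "then 294 patients (147 per study arm) are required for statistical power of 80" per cent.

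Section 11.2.2 states a between-arm hypothesis and section 8.4 randomises 1:1 in parallel groups. Section 11.2.3 says "Data analyses are powered to undertake Mixed Model Repeated Measures analyses to examine intervention effects on change from baseline to follow-up for each outcome", with a first model that accounts for baseline. The synopsis repeats the sample size only: "294 participants in total (in order to achieve 147 participants per study arm"; it gives no power.

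**The concern.** A paired t-test asks whether the mean change within one group differs from zero. It cannot compare mean change between two independently randomised arms, where the variance of the difference is the sum of both arms' variances. With equal arms and the same SD of change, the between-arm test needs twice as many evaluable patients in each arm.

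The rationale (section 3) says the trial is needed to establish efficacy on distress against an inactive control, and section 2 reports that the earlier trial found no significant difference in distress. The power attached to the 1.4-unit difference therefore governs how a non-significant result can be read. If the real power at the visit tested is near one half, a null result says little about whether an effect of 1.4 exists, yet the protocol would describe the trial as 80% powered for it.

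**Working it through.** **Inputs, all from section 11.1:** difference 1.4 (0.35 × 4); SD 7; r = 0.7; two-sided alpha 0.05; power 80%; attrition 20%; 147 per arm. The SD of 7 is read as the SD at each visit, because that is the reading that yields the protocol's 5.42.

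**1. Reproducing the protocol's figure**
- SD of change = 7 × √(2 × (1 − 0.7)) = 7 × √0.6 = 5.42. This matches.
- One-group (paired) normal formula: ((1.960 + 0.842) × 5.42 / 1.4)² = 117.6 pairs.
- Allowing for attrition: 117.6 / 0.8 = 147.0. This matches the stated per-arm number; 2 × 147 = 294.
- The exact paired t gives 120 pairs, or 150 after attrition, so the conclusion does not turn on the approximation.

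**2. Same inputs, two independent groups**
- Change scores: 2 × 117.6 = 235.3 evaluable per arm; 235.3 / 0.8 = 294 randomised per arm, about 588 in total.
- Baseline-adjusted: residual SD = 7 × √(1 − 0.7²) = 7 × √0.51 = 5.00. This needs 201 evaluable per arm; 201 / 0.8 is about 252 per arm, or 504 in total.

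**3. Power of the planned size at one visit**
- Evaluable per arm: 147 × 0.8 = 117.6.
- Change scores: standard error = 5.42 × √(2/117.6) = 0.707; 1.4 / 0.707 = 1.98. Power is 50.8% (noncentral t 50.5%).
- Baseline-adjusted: standard error = 5.00 × √(2/117.6) = 0.652; 1.4 / 0.652 = 2.15. Power is 57.4% (noncentral t 57.1%).
- Difference detectable at 80% power: 2.802 × 0.707 = 1.98 units, or 2.802 × 0.652 = 1.83 units.

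**4. Do the protocol's margins restore 80% at one visit?**
- No attrition, 147 per arm: 60% (change scores) or 67% (baseline-adjusted).
- Full 30% over-recruitment (section 8.10): 294 × 1.3 = 382, 191 per arm, about 153 evaluable. Power is 61% or 68%.

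**5. A baseline-adjusted average over k post-baseline visits**

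Assumed here, not stated in the protocol: the same r between every pair of visits and a constant effect of 1.4. SD = 7 × √((1 + (k − 1)r)/k − r²), with 117.6 evaluable per arm; power by noncentral t.

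| Visits averaged | r = 0.7: SD | Power | r = 0.5: SD | Power |
|---|---|---|---|---|
| 1 | 5.00 | 57% | 6.06 | 42% |
| 3 | 3.90 | 78% | 4.52 | 66% |
| 4 | 3.74 | 82% | 4.29 | 70% |

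**The case against.** The strongest defence is that the planned analysis is not a single-visit test. Section 11.2.3 plans a repeated-measures mixed model, there are four post-baseline assessments, and no section fixes one visit as primary. A reader might infer from the single-visit figures that this design cannot have 80% power for 1.4 units. The documents do not support that: a baseline-adjusted average over all four visits reaches about 82% under the assumptions in step 5. With full over-recruitment, the three-visit average would reach about 88% at r = 0.7 and 77% at r = 0.5. A mixed model also uses the earlier visits of patients who later drop out, so counting only 117.6 per arm is somewhat pessimistic for an averaged contrast.

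All of that stands as a limit on the claim, but it does not rescue section 11.1. The section names a paired t-test, contains no mixed-model calculation and mentions no averaging. Arriving near 80% that way also depends on a constant effect that includes the mid-point visit, which falls during treatment.

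Two further points are fair. The 51% and 57% depend on the stated attrition and on reading 7 as the SD at each visit; the text calls it a residual SD, although the derivation of 5.42 uses it as a per-visit SD. And because the correct two-group requirement is 294 per arm, a reader might infer that a per-arm result was copied as the total. That is only a numerical coincidence of 2 × 147; the text shows a one-group number applied to each arm and does not reveal how that came about.

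Deferral to a statistical analysis plan is no answer, since the protocol itself states a test, a sample size and a power that do not fit together.

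**Conclusion.** The point holds in a bounded form. The paired t-test in section 11.1 does not support 80% power for the between-arm comparison that the same section poses. At a single visit, after 20% attrition, power for 1.4 units is about 51% on change scores or 57% baseline-adjusted, and 80% power applies to about 1.98 or 1.83 units. Neither zero attrition nor full over-recruitment restores 80% at one visit under the protocol's inputs.

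Across the contrasts the planned model could yield at r = 0.7, power runs from about 51% to 82%, and the protocol does not say which contrast it means. The upper end rests on equal correlation between all visits and a constant effect, neither of which the protocol states. The stated justification is wrong as written and bears on the primary outcome, so it should be corrected.

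**What to change.** In section 11.1, replace the paired t-test with a two-independent-group calculation, or with an explicit mixed-model one. Keep 294 patients and restate the power for the contrast actually intended. For one visit after 20% attrition, that is about 51% on change scores or 57% baseline-adjusted for 1.4 units, or 80% for about 1.8 to 2.0 units. State that 7 is taken as the SD at each visit.

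If the sponsor intends a contrast averaged over visits, name the visits and quote its power together with the correlation and constant-effect assumptions, including a lower correlation such as 0.5. Adopting such a contrast is the sponsor's option and not part of this correction: it would define the primary contrast, which goes beyond rewording 11.1.

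The synopsis states no power and needs no change. No patients or data are added. The costs are a less favourable power statement and, under section 14.8, the approvals that any protocol amendment requires.
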